4.13. Discontinuation of Voruciclib Administration

Subjects may continue to receive voruciclib monotherapy or voruciclib + venetoclax combination therapy provided there is evidence of clinical response (PR or better) by the end of Cycle 6. Subjects may discontinue voruciclib monotherapy or voruciclib + venetoclax combination therapy for reasons including the following:

- Documented progression of disease while receiving therapy
- Unacceptable AE(s) considered secondary to voruciclib despite appropriate therapy and/or dose modification
- Intercurrent illness that precludes continued study therapy
- Withdrawal of consent by the subject
- Changes in the subject's medical condition that render further administration of voruciclib unacceptable in the judgment of the Principal Investigator or sponsor
- Treatment of the disease with another therapeutic regimen
- Pregnancy or breastfeeding
- Substantial noncompliance with study procedures
- Termination of study by the sponsor

4.14. Prohibited Treatments and Concomitant Medications – Cautions and Prohibitions

4.14.1. Concomitant Medications with Voruciclib – Cautions and Prohibitions

In vitro studies have shown that voruciclib has the potential to inhibit cytochrome (CYP) CYP2C9, CYP2C19, CYP2D6, and CYP3A4, therefore, drugs with a narrow therapeutic

window that are metabolized by these enzymes should be avoided or used with caution (see [Appendix 7](#)).

Subjects receiving warfarin treatment are excluded, since voruciclib is highly protein bound and is a competitive inhibitor of CYP2C9 at higher concentrations and increased INR was a DLT in the previous Phase 1 studies. Subjects on study who initiate warfarin therapy must discontinue voruciclib.

Consistent with subject safety and comfort, administration of any prescription or over-the-counter (OTC) drug products other than study medication will be minimized during the study period. Subjects should be discouraged from use of herbal remedies, self-prescribed drugs, tobacco products, or street drugs during their participation in the clinical study and should be counseled to minimize use of alcohol or nonmedical marijuana.

If considered necessary for the subject's well-being, drugs for concomitant medical conditions or for symptom management may be given at the discretion of the Investigator. The Investigator's decision to authorize the use of any drug other than study drug will take into account subject safety, the medical need, the potential for drug interactions, the possibility for masking symptoms of a more significant underlying event, and whether use of the drug will compromise the outcome or integrity of the study.

Subjects will be instructed about the importance of the need to inform the clinic staff of the use of any drugs or remedies (whether prescribed, OTC, or illicit) before and during the course of the study.

No other anti-cancer therapeutics or investigational agents are permitted during the study treatment period, except for hydroxyurea or anthracycline for the treatment of DS and to manage rapidly rising white blood cell counts in Cycles 1 and 2 only in patients with AML. Palliative radiotherapy is permitted after Cycle 1 but should be minimized and used for control of local tumor-related symptoms only.

If a subject experiences an AE, appropriate supportive care (e.g., antiemetics, antidiarrheals, antibiotics, granulocyte colony-stimulating factor [G-CSF] hydration) should be instituted consistent with the nature of the event. If the AE requires a dosing modification, the treatment regimen should be interrupted, as necessary. A decision should be made as to whether the subject can reasonably continue with the study drug based upon the nature and severity of the AE.

Recommendations regarding specific types of concomitant therapies, supportive care, diet, and other interventions are provided below. To minimize variations in supportive care, the recommended supportive care agents (e.g., loperamide, granisetron) should be used unless there is a medical rationale in a specific subject for use of an alternative product.

Antibiotics, Antifungals, Antivirals

Care should be taken to avoid or minimize concomitant administration of prophylactic or therapeutic antibacterial, antifungal, or antiviral agents that are moderate or strong CYP3A4 inhibitors or inducers. For subjects with CLL/SLL and a history of recurrent infections, prophylaxis with intravenous immunoglobulin may be offered and consideration may be given to initiation of antibiotic prophylaxis against pneumocystis infection (e.g., with trimethoprim-sulfamethoxazole, dapsone, aerosolized pentamidine, or atovaquone) beginning prior to study drug administration. Such support also offers the benefit of reducing the risk for other bacterial infections. Local practices or guidelines regarding infection prophylaxis may be followed.

Subjects developing an intercurrent infection during study drug treatment may receive therapeutic antibacterial, antiviral, or antifungal drugs for intercurrent infections as needed. Continuation of study therapy during treatment for an intercurrent infection is at the discretion of the Investigator. Given that voruciclib is a CYP3A4 substrate and the critical role of azole antifungals (commonly strong CYP3A4 inhibitors) in the treatment of fungal infections in patients with AML, voruciclib must be held during treatment with an azole and restarted when the azole therapy is completed. Antifungals other than azoles may be used if considered by the investigator as a clinically appropriate alternative to azoles.

In the voruciclib and venetoclax combination groups, antifungal prophylaxis (excluding azoles) may be provided according to institutional guidelines and in accordance with guidance for management of potential venetoclax interactions per the venetoclax PI ([Venclexta \[US Prescribing Information\] Rev 2022](#)) provided in [Table 13](#).

Of note, hepatitis B virus reactivation can occur in subjects previously treated with anti-CD20 therapeutic antibodies. The median time to diagnosis of hepatitis among subjects with hematologic malignancies is 4 months after the initiation of therapy, but such events can occur months after completion of anti-CD20 antibody therapy.

Anticoagulants

Use of systemic anticoagulants should be avoided unless necessary for a serious intercurrent thrombotic or embolic condition. Because voruciclib appears to increase exposure to warfarin, subjects receiving warfarin are ineligible for enrollment and subjects on study who start warfarin must discontinue voruciclib.

Antidiarrheals

Subjects experiencing diarrhea (and/or abdominal cramping) may take loperamide at the earliest sign of a loose stool, an increase in bowel movements by 1 to 2 episodes compared to baseline, or an increase in stool volume or liquidity. The recommended regimen is 4 mg at the first onset of diarrhea, and then 2 mg with each succeeding diarrheal stool until the subject is diarrhea-free for at least 12 hours.

Additional antidiarrheal measures may be implemented at the discretion of the Investigator. Subjects should also be instructed to maintain oral fluid intake to help sustain fluid and electrolyte balance during episodes of diarrhea.

Antiemetics

While prophylactic antiemetics can be considered, antiemetics should not be given prophylactically before initial study drug administration on Cycle 1 Day 1. Choice of antiemetic therapy should be based on standard practice and/or institutional guidelines.

Antihistamine, Anti-inflammatory, and Antipyretic Drugs

Antihistamines (e.g., cetirizine, diphenhydramine), and anti-inflammatory/antipyretic drugs (e.g., acetaminophen [paracetamol], nonsteroidal anti-inflammatory drugs [NSAIDs]), may be used during the study, as medically warranted.

Corticosteroids

At study entry, subjects may not be using enteric corticosteroids but may be receiving systemic corticosteroids (at doses of ≤ 20 mg/day of prednisone or equivalent) or topical or inhaled corticosteroids. During study therapy, subjects may use systemic, enteric, topical, or inhaled corticosteroids as required for treatment-emergent conditions.

Calcineurin inhibitors are prohibited during study treatment.

CYP3A4 Inhibitors and Inducers

Whenever possible moderate or strong inhibitors or inducers of CYP3A4 should be avoided and only administered if essential for patient care ([Appendix 7](#)).

Drugs Affecting Gastric pH

A potential effect of altering gastric pH on the absorption of voruciclib cannot be excluded. Proton pump inhibitors should be avoided if possible. Antacids and H₂-receptor antagonists should be taken at least 4 hours before or after voruciclib.

Drugs with a Narrow Therapeutic Range that are P-gp substrates

Based on in vitro studies, voruciclib may be a P-gp inhibitor; however, the clinical relevance of this finding is not known. Drugs with a narrow therapeutic range that are P-gp substrates should be avoided or used with caution (e.g., digoxin, colchicine).

Hematopoietic Support

Granulocyte colony-stimulating factor (G-CSF) (e.g., filgrastim, filgrastim-snd, peg-filgrastim, lenograstim) may be administered in response to Grade ≥ 3 neutropenia or neutropenic complications.

Granulocyte-macrophage colony-stimulating factor (GM-CSF) should not be administered, given the potential for GM-CSF-related inflammatory symptoms.

Erythropoietic agents (e.g., erythropoietin or darbepoetin) may be administered for Grade ≥ 3 anemia, at the discretion of the treating physician.

Red blood cell or platelet transfusions may be administered as medically indicated.

Drugs Known to Prolong QT Interval

The effect of voruciclib on the QT interval has not been determined, therefore, drugs known to prolong QT interval should be avoided, if possible (ondansetron use is acceptable). See [Appendix 8](#) for a list of medications known to prolong the QT/QTc interval.

Immunization

For subjects who are at risk of an infection (e.g., influenza, herpes zoster) that might be prevented by immunization, consideration should be given to providing the vaccine prior to initiation of study therapy.

Immunization for the SARS-CoV-2 virus, responsible for COVID-19 infection, may be performed according to institutional guidelines.

Whether voruciclib would increase the risk of live viral vaccines during study therapy is unknown. Pending the acquisition of additional information, live viral vaccination should be avoided 10 days prior to first dose and during study therapy.

Do not administer live attenuated vaccines prior to, during, or after treatment with venetoclax until B-cell recovery occurs. The safety and efficacy of immunization with live attenuated vaccines during or following venetoclax therapy have not been studied. Advise patients that vaccinations may be less effective ([Venclexta \[US Prescribing Information\] Rev 2022](#)).

Cytoreductive Therapy in AML patients

Cytoreduction with hydroxyurea (or another cytoreductive therapy) must be implemented prior to initiating voruciclib, or venetoclax in Cohorts 12–25, if the subject has white blood cell counts $\geq 25 \times 10^9/L$.

In subjects with rapidly rising white blood cell counts in Cycles 1 and 2, a short course of hydroxyurea (or another cytoreductive therapy) may be administered at the discretion of the Investigator to control rising cell counts while continuing study drug(s) administration.

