In Amendment 11, subsequent to determination of the safe and mBED of voruciclib monotherapy in AML subjects, the combination of voruciclib with venetoclax will be evaluated in subjects with relapsed and/or refractory AML (see rationale provided below).

The combination cohorts, beginning at Cohort 12 dose level of voruciclib in combination with venetoclax on an IS_{2w,2w} dosing schedule, will be enrolled as follows:

- Cohort 12: 50 mg once every other day (QOD), administered IS_{2w,2w} + venetoclax administered QD × 28 days
- Cohort 13: 50 mg QD, administered IS_{2w,2w} + venetoclax administered QD × 28 days
- Cohort 14: 100 mg QD, administered IS_{2w,2w} + venetoclax administered QD × 28 days
- Cohort 15: 150 mg QD, administered IS_{2w,2w} + venetoclax administered QD × 28 days
- Cohort 16: 200 mg QD, administered IS_{2w,2w} + venetoclax administered QD × 28 days
- Cohort 17: 250 mg QD, administered IS_{2w,2w} + venetoclax administered QD × 28 days
- Cohort 18: 300 mg QD, administered IS_{2w,2w} + venetoclax administered QD × 28 days
- Cohort 19: 350 mg QD, administered IS_{2w,2w} + venetoclax administered QD × 28 days

Dose escalation to the next cohort will be reviewed by the SRC after 3 subjects have completed 1 cycle with no reported DLTs, or after 6 subjects have completed 1 cycle with no more than 1 DLT. (DLT criteria defined below.) Escalation to a subsequent cohort will depend on demonstrated safety and tolerability within a cohort and with the approval of the SRC.

If the next dose level in the AML combination cohort has been declared safe by the SRC, subjects enrolled at a lower dose level may have their dose escalated to the next dose level after completing Cycle 1 without a DLT (intra-subject dose escalation). For example, a subject with AML enrolled in Cohort 13 (50 mg IS_{2w,2w}) may have the dose increased to 100 mg in Cycle 2 if the dose of 100 mg IS_{2w,2w} was deemed safe in Cohort 14 by the SRC.

Dose escalation proceeds until a real-time assessment of clinical and PK parameters by the SRC establishes the safe and mBED for voruciclib in combination with venetoclax. More specifically, a voruciclib dose in combination with venetoclax that meets the following criteria:

- DLT not to exceed 1 in 6 subjects, overall response rate (ORR) ≥30%, as compared to historical ORR of 19% with 400-800 mg venetoclax alone in relapsed/refractory AML ([Konopleva 2016](#)), and

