- Trough plasma concentration of 1 to 1.5 μM , concentrations shown to be synergistic in combination with venetoclax in preclinical models.

In Amendment 12, the combination of voruciclib with venetoclax will be evaluated in subjects with relapsed and/or refractory AML using a voruciclib intermittent schedule of daily dosing on Days 1–21 in a 28-day cycle, with no voruciclib dosing on Days 22–28 of the cycle, designated as $\text{IS}_{3\text{w},1\text{w}}$. (see rationale below). In Cycle 1, voruciclib dosing begins on Day 3 after completion of venetoclax dose ramp-up. The starting voruciclib dose level on $\text{IS}_{3\text{w},1\text{w}}$ will be 150 mg (i.e., 2 dose levels lower than the dose of 250 mg that was shown to have no DLTs in the $\text{IS}_{2\text{w},2\text{w}}$ schedule). The venetoclax dose will be 200 mg on Days 1–21 and 400 mg on Days 22–28 in a 28-day cycle. In Cycle 1, venetoclax dose ramp-up will consist of venetoclax 100 mg on Day 1, then 200 mg on Days 2–21, then 400 mg on Days 22–28, with voruciclib beginning on Day 3. Dose escalation will follow the same 3+3 design as in the $\text{IS}_{2\text{w},2\text{w}}$ cohorts, and uses the same definition for DLT, MTD, and mBED.

In the $\text{IS}_{2\text{w},2\text{w}}$ dose escalation cohorts, no DLTs have been reported at doses ranging from 50 mg QOD to 250 mg QD, and enrollment was ongoing at the 300 mg dose level at the time of issuance of protocol Amendment 12.

The combination cohorts on $\text{IS}_{3\text{w},1\text{w}}$ will be numbered as listed below:

- Cohort 21: 150 mg QD, administered $\text{IS}_{3\text{w},1\text{w}}$ + venetoclax administered QD \times 28 days
- Cohort 22: 200 mg QD, administered $\text{IS}_{3\text{w},1\text{w}}$ + venetoclax administered QD \times 28 days
- Cohort 23: 250 mg QD, administered $\text{IS}_{3\text{w},1\text{w}}$ + venetoclax administered QD \times 28 days
- Cohort 24: 300 mg QD, administered $\text{IS}_{3\text{w},1\text{w}}$ + venetoclax administered QD \times 28 days
- Cohort 25: 350 mg QD, administered $\text{IS}_{3\text{w},1\text{w}}$ + venetoclax administered QD \times 28 days

Expansion Cohorts

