 - b. Total bilirubin $\leq 1.5 \times \text{ULN}$ (if secondary to Gilbert's syndrome, $\leq 3 \times \text{ULN}$ is permitted)
 - c. Creatinine clearance ≥ 60 mL/minute
11. Subjects with B-cell malignancies must have completed:
 - a. Previous anti-cancer medication a minimum of 5 elimination half-lives ($t_{1/2}$) or 2 weeks (whichever is less) prior to Day 1 (a course of corticosteroids ≤ 7 days in duration prior to Day 1 is allowed)
 - b. Radiation therapy or surgery ≥ 2 weeks before Day 1
12. Subjects with AML must have completed:
 - a. Previous anti-cancer medication for a minimum of 5 elimination half-lives ($t_{1/2}$) or 2 weeks (whichever is less) prior to start of voruciclib (monotherapy) or venetoclax (combination therapy) administration
 - b. Radiation therapy ≥ 2 weeks or major surgery ≥ 4 weeks before start of voruciclib (monotherapy) or venetoclax (combination therapy) administration

Note: Hydroxyurea and other therapy to control leukocytosis is allowed up to the end of Cycle 1
13. All clinically significant treatment-related toxicity from prior therapy (other than alopecia) must have resolved to Grade ≤ 1 , or to a new stable baseline at time of enrollment
14. Females of childbearing potential must have a negative serum pregnancy test within 14 days prior to Day 1
15. For subjects capable of procreation, agree to use medically effective contraception during the study (which must, at the minimum, include a barrier method), and for 90 days after discontinuation of study drug. Females of childbearing potential should use 2 forms of contraception, one of which should be a barrier contraceptive
16. Agree to not donate sperm or oocytes during the entire study treatment period, and for 90 days after study drug discontinuation

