4.10. Differentiation Syndrome

Differentiation syndrome (DS) is a relatively common and potentially severe complication seen in patients with acute promyelocytic leukemia treated with all-trans retinoic acid and/or arsenic trioxide. The syndrome includes, but may not be limited to, unexplained fever, weight gain, dyspnea with pulmonary infiltrates, pleuro-pericardial effusion, hypotension, and/or renal failure. Cases of DS have been recently reported in patients with various types of AML administered FMS-like tyrosine kinase 3 (Flt3) inhibitors and isocitrate dehydrogenase (IDH) inhibitors.

Although the pathogenesis of DS has not been entirely clarified, it has been speculated it is due to a cascade of pathophysiologic mechanisms, leading to a systemic inflammatory response syndrome, endothelium damage with capillary leak syndrome, occlusion of microcirculation, and tissue infiltration with leukocytes. In this study, a diagnosis of DS should be suspected in subjects with AML in the presence of any of the above-mentioned signs and symptoms, and preemptive treatment with dexamethasone should be started immediately, particularly in patients with leukocyte counts greater than $10,000/\mu L$. Other supportive measures can also be crucial for

the correct management of DS, especially in patients with life-threatening complications (Sanz 2014). Temporary interruption of voruciclib is indicated for patients in poor clinical condition. Treatment with hydroxyurea (or an anthracycline if appropriate) to control rising leukocyte counts is also recommended.

Two subjects with AML enrolled in Cohort 2 (monotherapy) of this study experienced symptoms consistent with DS in Cycle 1 of voruciclib administration, including fever, hypoxemia, pulmonary infiltrate, and pleural effusion. The mechanism by which voruciclib may induce DS is unclear. Investigators should be aware of DS as differential diagnosis in patients with AML experiencing fever, pulmonary or hemodynamic complications in the first weeks of voruciclib administration. After ruling out an infection or other causes, treatment with dexamethasone and supportive care measures is recommended. Hydroxyurea (1-2 g/day) or an anthracycline (if appropriate) can be used to control rising leukocyte counts.

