**Table 5-2: Date of Progression or Censoring for PFS**

| Situation  | Date of progression or censoring   | Outcome  |
|--|--|----------|
|  |  |          |
| Death or disease progression   | Date of death or first disease assessment (planned or unplanned) showing disease progression, whichever occurs first | Event    |
| No evaluable disease assessments   | Date of the first dose   | Censored |
| Subsequent anticancer treatment started before the first documented disease progression or death | Date of last disease assessment prior to the subsequent anticancer treatment   | Censored |
| Alive and without disease progression on or before EOS visit                                     | Date of last disease assessment  | Censored |

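### AML response rate has no rule for remissions that follow permitted on-study cytoreduction, so the ≥30% ORR component of the mBED decision can be inflated

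*Protocol*

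**What the plan says.** **Permission.** Protocol Section 4.14.1 prohibits other anti-cancer drugs during study treatment "except for hydroxyurea or anthracycline for the treatment of DS and to manage rapidly rising white blood cell counts in Cycles 1 and 2", for AML only. Its later paragraph on cytoreductive therapy says that, when counts rise rapidly in those cycles, "a short course of hydroxyurea (or another cytoreductive therapy) may be administered at the discretion of the Investigator". The sentence goes on to give the aim, which is to "control rising cell counts while continuing study drug(s) administration". The note to inclusion criterion 12 (Section 3.1 and synopsis) has a shorter window: "Hydroxyurea and other therapy to control leukocytosis is allowed up to the end of Cycle 1". The differentiation syndrome (DS) guidance in Section 4.10 adds: "Hydroxyurea (1-2 g/day) or an anthracycline (if appropriate) can be used to control rising leukocyte counts".

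**Response timing.** For combination cohorts, Protocol Section 9.7 and Appendix 3 schedule marrow on Cycle 2 Day 1 and on Day 1 of each later cycle until CR or CRi.

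**Response rate.** Protocol Section 10.2 and SAP Sections 5.1.2 and 8.6.2 define AML ORR by best overall response: CR, CRi, CR without minimal residual disease, or MLFS. SAP Section 8.6.2.1 derives it from CR/CRi or PR instead. SAP Section 6.3 (Efficacy Evaluable Set) excludes nobody for cytoreduction. The SAP deals with other anti-cancer treatment only for DOR and PFS. The PFS table, for example, has a censoring row for "Subsequent anticancer treatment started before the first documented disease progression or death".

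**Use of ORR.** The synopsis sets the mBED conditions, repeated in substance in Protocol Section 4.3.2 and SAP Section 3.1.1: "DLT not to exceed 1 in 6 subjects, overall response rate (ORR) ≥30%, as compared to historical ORR of 19" per cent, and a trough of 1 to 1.5 µM, "concentrations shown to be synergistic in combination with venetoclax in preclinical models".

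**The concern.** An anthracycline is active against leukaemia in its own right. If it is given in Cycle 1 or 2, the next scheduled marrow falls inside or just after that treatment. A CR, CRi or MLFS found there may owe something to the added agent, but the plan as written credits it to voruciclib plus venetoclax. There is no control arm in which the same effect would cancel, and the resulting rate is held against 30% and a historical 19%.

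MLFS adds to the exposure. Under Appendix 4 it requires no blood-count recovery, so marrow clearance alone counts under the definition in SAP Section 5.1.2 (though not under the derivation in Section 8.6.2.1).

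At stake is one component of the decision that stops escalation and may open expansion, taken on very few subjects.

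**Working it through.** **1. The plan's own figure.** Protocol Section 1 reports 2 CR and 4 CRi among 32 patients on venetoclax alone: (2 + 4)/32 = 18.75%, which rounds to the stated 19%.

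**2. Search for a rule.** These places could hold a rule on cytoreduction for ORR: the definitions (Protocol 10.2; SAP 5.1.2, 8.6.2), the derivation (SAP 8.6.2.1), the efficacy set (Protocol 10.3.2; SAP 6.3), missing data (SAP 7.4) and dose-modified subjects (SAP 7.6). None makes a subject treated with cytoreduction a non-responder, ends response assessment at that treatment, or asks for a sensitivity analysis.

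**3. Responses needed.** Escalation is reviewed on 3 or 6 subjects (Protocol 4.3.2), and a fourth may be enrolled (Protocol 4.1). The number needed, r, is the smallest count with r/n ≥ 0.30. The documents give no alpha, power or sample size for this criterion, so exact binomial probabilities are used with a true ORR of 19%:

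- P(meets) = P(X ≥ r), X ~ Bin(n, 0.19)
- P(one short) = P(X = r − 1)
- P(meets, one subject counted because of cytoreduction) = P(Y ≥ r − 1), Y ~ Bin(n − 1, 0.19)

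| n | r | One short → met | P(meets) | P(one short) | P(meets, one subject so counted) |
|---|---|---|---|---|---|
| 3 | 1 | 0/3 (0%) → 1/3 (33.3%) | 0.469 | 0.531 | 1.000 |
| 4 | 2 | 1/4 (25.0%) → 2/4 (50.0%) | 0.166 | 0.404 | 0.469 |
| 6 | 2 | 1/6 (16.7%) → 2/6 (33.3%) | 0.320 | 0.397 | 0.651 |

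For n = 6: P(one short) = 6 × 0.19 × 0.81⁵ = 0.397, and the last column is 1 − 0.81⁵ = 0.651. That column is conditional on such a remission occurring. It is not a forecast.

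**4. Size under an assumption.** The documents give neither the frequency of cytoreduction nor how often it produces a remission. Assume, for illustration only, that a fraction q = 10% to 30% of subjects receive it and that it converts c = 20% to 50% of those who would not otherwise respond. The apparent ORR is 0.19 + 0.81 × q × c:

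- low end: 0.19 + 0.81 × 0.10 × 0.20 = 20.6%; P(meets) at n = 6 is 0.360
- high end: 0.19 + 0.81 × 0.30 × 0.50 = 31.2%; P(meets) at n = 6 is 0.604

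The value without any such effect is 0.320.

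**5. Windows and agents side by side.**

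| Place | Agents | Window |
|---|---|---|
| Inclusion 12 note (synopsis, 3.1) | hydroxyurea and other leukocytosis therapy | to end of Cycle 1 |
| 4.14.1, general rule | hydroxyurea or anthracycline | Cycles 1 and 2 |
| 4.14.1, cytoreduction paragraph | hydroxyurea or another cytoreductive agent | Cycles 1 and 2 |

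Cycle 2 use fits the last two rows but not the first. An agent other than hydroxyurea or an anthracycline fits the first and third but not the second.

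**The case against.** Several stronger readings are tempting, and the documents do not support them.

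- **A reader might infer that cytoreduction alone can get a dose declared the mBED.** It cannot. ORR is joined with the DLT limit and the trough range, and the SRC, which includes clinical investigators, judges them together. It could discount a doubtful remission, though no text tells it to.
- **A reader might infer that one response is decisive at every cohort size, including 3/12 to 4/12 in expansion.** Expansion opens only after the mBED is declared (Protocol 4.3.2, 4.5), and no passage applies the 30% criterion to it. Within escalation, one response matters only when the cohort is exactly one short.
- **A reader might infer a known upward bias.** The documents offer no rate. The stated uses are DS and rising counts, by a short course in the latter case. Subjects must also be ineligible for, or have failed, other therapies known to be effective (criterion 4b).
- **A reader might see Section 4.10 as a further contradiction.** It is DS guidance for the first weeks of treatment. Its silence on cycles does not conflict with the general limit in Section 4.14.1.
- **A reader might infer that PFS would be censored at or near baseline.** The protocol uses subsequent or new anti-cancer therapy as the point where adverse-event collection ends (Sections 6.4, 9.5). Permitted cytoreduction given alongside study drug most naturally falls outside that term. The SAP simply does not say so.

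Counting response regardless of added treatment is also a legitimate choice, and strict non-response has its own error: one true responder treated for DS turns 2/6 into 1/6. SAP Section 7.9 calls the study exploratory.

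These points limit the reach of the concern and shape the remedy. They do not supply the missing rule, and the exploratory label does not remove ORR from the dose decision.

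**Conclusion.** The concern holds in a limited form. The plan permits an anthracycline or another cytoreductive agent in Cycles 1 and 2, scores marrow from Cycle 2 Day 1, and counts best response whatever was given. A remission first documented after such an agent therefore enters the AML ORR as a response to the study regimen.

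The firm part of the size is arithmetic: in a cohort of 3, 4 or 6 that is one response short, one such remission moves the ORR component from not met to met. The chance of being one short is 0.531, 0.404 and 0.397 respectively, if the true ORR is 19% and all subjects in the cohort are evaluable. The rise in P(meets) at n = 6 from 0.320 to between 0.360 and 0.604 rests wholly on the assumed range in step 4. Actual frequency, and so actual bias, is unknown.

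The conflict between the inclusion note and Section 4.14.1 is real and separate from the size of any bias.

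**What to change.** 1. **SAP Sections 5.1.2 and 8.6.2.1.** Pre-specify an AML ORR in which a subject whose first response follows an on-study anthracycline or other non-hydroxyurea cytoreductive agent stays in the denominator as a non-responder. Report it beside ORR counted regardless of that agent, and flag responders who had hydroxyurea. Use one AML response definition in both sections.
2. **SRC review.** Give the SRC both figures when it considers the mBED.
3. **SAP Tables 5-1 and 5-2.** State whether permitted on-study cytoreduction counts as subsequent anti-cancer treatment.
4. **Protocol.** Reconcile the inclusion 12 note (synopsis and Section 3.1) with the two statements in Section 4.14.1 on window and agents. Which window and agents apply is for the sponsor. The statistical change does not require any clinical permission to change.

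**Cost.** SAP wording, one extra table line and a protocol clarification. Concomitant medications are already collected and listed (Protocol 9.3; SAP 8.4), and SAP Section 7.4 already handles their partial dates. The stricter ORR may be lower and could misclassify a true responder who was treated for DS, which is why both figures should be shown.
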